11.2 Statistical Methods

11.2.1 Methods of Analysis

Verbatim AE terms will be coded using the Medical Dictionary for Regulatory Activities (MedDRA). The number and percentage of patients who experience AEs and SAEs will be summarized by dose/treatment group and overall.

Laboratory, vital sign, ECG, and efficacy data will be summarized descriptively (mean, median, standard deviation [SD], and minimum and maximum values) by dose/treatment group and overall and will be summarized by protocol specified time point along with a summary of change from baseline at each protocol specified time point. Changes in physical examinations will be listed for each patient and described.

PK analyses will include determination of plasma levels of KZR-616 including C_{\max} , T_{\max} , and AUC.

All patients who receive any amount of study drug (Safety Population) will be included in the safety analyses. Descriptive statistics, including the numbers and percentages for categorical variables and the numbers, means, SDs, medians, minimums and maximums for continuous variables will be provided by dose/treatment group overall.

11.2.2 *Analysis Population*

Safety Population

All patients who receive any amount of study drug will be included in the safety analyses.

PK Analysis Population

All patients who receive the Day 1 dose of KZR-616 and who have at least one post-dose concentration of KZR-616 measured will be included in the PK analysis population. Any protocol deviations affecting PK analyses may result in exclusion from summaries for individual time point concentrations, complete profiles, and/or PK parameters. These exclusions will be reviewed before database lock and confirmed with the sponsor before the implementation.

Pharmacodynamics Analysis Population

All patients who receive any amount of study drug and who have any measured results for PD assessment will be included in the PD analysis population. Any protocol deviations affecting PD analyses may result in exclusion from summaries for individual time point concentrations and/or complete profiles. These exclusions will be reviewed before database lock and confirmed with the sponsor before the implementation.

11.3 Assessments

11.3.1 *Criteria for Evaluation – Safety Analysis*

Safety and tolerability is the primary endpoint for Phase 1b and a secondary endpoint for Phase 2.

Safety for the study will be evaluated through monitoring and assessment of all AEs, physical examination findings, vital sign measurements (blood pressure, pulse, and body temperature), ECGs, and clinical laboratory test results (hematology, serum chemistry, urinalysis) including quantitative serum immunoglobulins.

Severity of AEs will be assessed using the NCI-CTCAE, Version 4.03.

All AEs occurring on or after treatment on Week 1, Day 1 through Week 25, Day 169 for Phase 1b and through Week 37, Day 253 for Phase 2 will be summarized by MedDRA system organ class, preferred term, grade, and investigator assessment of causality.

In addition, all SAEs, including deaths, will be listed separately and summarized. Extent of exposure to the study treatment will be summarized using descriptive statistics.

Full details of the analyses will be specified in the statistical analysis plan (SAP). With regard to inconsistencies, the SAP will take precedence over the protocol.

11.3.2 Criteria for Evaluation – Pharmacokinetic Analyses

Phase 1b:

Assessment of the Secondary Endpoint:

Blood samples will be collected from all patients to measure the plasma concentration of KZR-616 on Days 1 and 29 of Weeks 1 and 5, respectively. Blood samples will be collected before dosing and 5, 15, 30 minutes and 1, 2, 4, and 8 hours after the injection. Plasma PK parameters, including C_{max} , T_{max} , AUC from time 0 to the last measured concentration (AUC_{last}), and other applicable parameters such as elimination parameters data permitting, will be calculated for KZR-616. The PK parameters will be listed and summarized by dose/treatment group and type of the disease as applicable. Dose proportionality assessments and other comparisons such as effect of the type of disease may be performed.

Concentrations will be listed and summarized for all patients by dose level and type of the disease as applicable. The excluded data will be flagged and explained in the footnotes.

Urine PK of the drug will be analyzed from urine samples pooled from 0 to 8 hours post-dose (see [Section 8.3](#)). Total amount of excreted unchanged and metabolized drug (A_e) and percent fraction of dose excreted (%Fe) will be listed and summarized by dose/treatment group and type of disease, where applicable. Exploratory correlation between %Fe and eGFR may be evaluated.

The PK results will be presented graphically as individual and mean plasma concentration plots. Statistical models will be presented by regression plots vs dose and box plots for different treatments. The details of the analysis will be further described in the SAP.

11.3.3 Criteria for Evaluation – Pharmacodynamic Analyses

Pharmacodynamic analyses will be performed in both Phase 1b and Phase 2. The extent of proteasome activity in whole blood and isolated PBMCs will be assessed in blood samples collected.

The PD effects of KZR-616 will be assessed by evaluating levels of proteasome activity. Proteasome CT-L peptidase activity will be measured by a cleavable fluorogenic substrate enzymatic activity assay. The inhibition of proteasome activity will be expressed relative to

individual patient matched pre-dose levels in whole blood and PBMCs, representing selective inhibition of constitutive proteasome and immunoproteasome, respectively.

KZR-616 occupancy of individual subunits of proteasome in whole blood and PBMCs is measured by subunit-specific proteasome active site ELISA (ProCISE). KZR-616 occupancy/ inhibition of constitutive and immune-proteasome specific subunits will be expressed relative to individual patient matched pre-dose levels. ProCISE will further confirm selective inhibition of constitutive proteasome and immunoproteasome by KZR-616.

11.3.4 Criteria for Evaluation – Biomarker and Other Analyses

Obtain material to assess gene transcriptional and proteomic changes following KZR-616 treatment including (i.e., RNA) profiling through ex vivo analysis of whole blood and PBMC samples. In the Phase 1b, blood samples will be collected on Day 1 of Weeks 1, 5, 17, and 25 (For DNA genotyping a sample will be collected only on Day 1, Week 1). In the Phase 2, blood samples will be collected on Day 1 of Weeks 1, 17, 25, and 37 (For DNA genotyping a sample will be collected only on Day 1, Week 1).

The immunomodulatory activity of KZR-616 will be assessed by evaluating levels of cytokines, including change from baseline.

11.3.5 Criteria for Evaluation – Efficacy Analyses

Phase 2:

Assessment of Primary and/or Secondary Endpoints

Please see [Section 11.1.2](#) for a listing of secondary endpoints for Phase 2.

Rate of renal response will be assessed at 24 weeks. Renal response will be classified as complete, partial [50% reduction in UPCR], or no renal response. Summary statistics (e.g., total number of patients with observed data, mean, median, SD, min, max for continuous endpoints; for binary endpoints: total number of patients observed, number of patients with the event of interest, percent) will be provided by dose in Phase 1b and for all patients combined in Phase 2. The primary efficacy endpoint in Phase 2 is percent of patients with 50% reduction in UPCR after 24 weeks of treatment when compared to baseline. The null hypothesis is that the percentage is $\leq 20\%$; the alternative hypothesis is that the percentage is $> 20\%$. The test of hypotheses will be carried out with an exact binomial test. The KZR-616-002 Statistical Analysis Plan contains details of the planned analysis.

Phase 1b and Phase 2: Exploratory Endpoints:

The efficacy of KZR-616 on SLE will be assessed using changes from baseline in study administered questionnaires/disease assessment tools and changes from baseline in laboratory measures.

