Pharmacodynamics: Blood samples for the determination of proteasome activity in whole blood and peripheral blood mononuclear cells will be assessed in blood samples collected as follows:

Phase 1b – Day 1 of Week 1 and Week 5, before dosing and 4 hours after

Phase 2 – Day 1 of Week 1, before dosing and 4 hours after injection, and Day 1 of Week 5, before dosing

Biomarkers: Blood samples for the determination of serum cytokine levels and circulating leukocytes will be measured in blood samples collected as follows:

Phase 1b – Day 1 of Weeks 1, 5, 17, and 25

Phase 2 – Day 1 of Weeks 1, 17, 25, and 37

Pharmacogenomics:

Gene expression (RNA) profiling – Blood samples collected as follows:

Phase 1b – Day 1 of Weeks 1, 5, 17, and 25

Phase 2 – Day 1 of Weeks 1, 17, 25, and 37

DNA genotyping – Day 1 of Week 1

Endpoints

Phase 1b:

Primary Endpoint:

- Safety and tolerability of KZR-616 as assessed by incidence, nature, and severity of AEs

Secondary Endpoints:

- The RP2Ds of KZR-616 as determined by evaluation of safety parameters, PK, PD, and DLTs by the DMC
- Plasma PK parameters, including maximum plasma concentration (C_{max}), time to maximum plasma concentration (T_{max}), area under the plasma concentration-time curve (AUC), and other applicable parameters will be calculated for KZR-616

Phase 2:

Primary Endpoint:

- The number of patients with a 50% reduction in UPCr after 24 weeks of treatment when compared to baseline

Secondary Endpoints:

- Safety and tolerability of KZR-616 as assessed by the incidence, nature, and severity of AEs
- The number of patients with a partial renal response (PRR) after 24 weeks of treatment as defined by:
 - a) A 50% reduction of UPCr and/or reduction of UPCr to < 1.0 if the baseline UPCr was < 3.0 or a 50% reduction of UPCr and/or reduction of UPCr to < 3.0 if the baseline was ≥ 3.0
 - b) eGFR of ≥ 60 mL/min/1.73 m² or no worsening of eGFR from baseline of $\geq 25\%$
 - c) No use of prohibited medication
- The number of patients with a complete renal response (CRR) after 24 weeks of treatment as defined by:
 - a) UPCr of ≤ 0.5
 - b) eGFR of ≥ 60 mL/min/1.73 m² or no worsening of eGFR from baseline of $\geq 25\%$

-
- c) Prednisone (or equivalent) ≤ 10 mg
 - d) No use of prohibited medication
 - Time to $\geq 50\%$ reduction in UPCR from baseline
 - Time to CRR
 - Time to PRR
 - The number of patients with UPCR of ≤ 0.5 at 24 weeks

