- In Phase 1b, if the baseline prednisone dose is ≥ 10 mg/day, tapering is strongly encouraged, and at the investigator's discretion. However, stable prednisone dose is required between Week 9 and Week 13.
- In Phase 2, if the baseline prednisone dose is ≥ 10 mg/day, tapering is strongly encouraged, and at the investigator's discretion to a goal of prednisone ≤ 10 mg/day (or prednisone equivalent) by Week 16. Stable prednisone dose is preferred between Week 16 and Week 24.
- Prednisone (or other corticosteroid) can be initiated or increased to treat a non-renal SLE flare when deemed necessary by the treating physician or clinical investigator.
- Intra-articular or intra-bursal corticosteroid injections are permitted when deemed necessary by the treating physician or clinical investigator.

Other Concomitant Medications

Other concomitant therapies for comorbid conditions, such as antihypertensives or lipid lowering agents, are permitted. The patient should be advised to maintain stable dosage regimen for antihypertensive medication(s) (such as angiotensin receptor blocker [ARB]/angiotensin-converting enzyme inhibitor [ACE-I]), lipid lowering agents (such as statins), NSAIDs unless the dosage adjustment is clinically necessary, e.g., to control hypertension or for intolerance.

KZR-616 is a substrate of the P-gp transporter. Given the rapid clearance of the drug (half-life < 2 hours), it is unlikely that inhibitors of P-gp will affect drug exposure. However, no formal interaction studies with P-gp inhibitors have been performed. Therefore, KZR-616 should be administered at least 6 hours before or 4 hours after drugs that are known inhibitors of P-gp (e.g., cyclosporine, atorvastatin, azithromycin, colchicine, omeprazole).

Vaccinations

It is strongly recommended that patients be up-to-date on immunizations per current 2015 ACR guidelines for RA.⁴⁵ Vaccinations received at any time documenting that the patient is up-to-date on vaccines should be recorded in the eCRF.

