7.2.2 Required Concomitant Medications

Phase 1b:

Patients should remain stable on their medications during the treatment period, per inclusion and exclusion criteria, [Section 7.2](#), and [Section 14.5](#), Appendix E.

Phase 2:

Patients should remain stable on their medications during the treatment period, per inclusion and exclusion criteria, [Section 7.2](#), (including [Table 3](#)) and [Section 14.5](#), Appendix E.

Permitted therapy for LN for study entry is listed in [Table 3](#) and should include at least one non-corticosteroid immunosuppressant. Additionally, one antimalarial and up to 60 mg prednisone or prednisone equivalent are permitted.

For those on a EuroLupus CYC regimen at study entry, once treatment course is complete (500 mg every 2 weeks for 6 doses, or similar), an appropriate immunosuppressive regimen should be initiated with a goal of stable dosing by Week 16, and stable dosing between Weeks 16 and 24.

Once enrolled, treatment regimens should not be changed except as above (including steroid taper) or for reasons of unavailability. Immunosuppressant(s) should not be added to current regimen except as above after completion of a EuroLupus CYC regimen. Corticosteroids should not be added during the study except when needed to treat an SLE flare, and antimalarials should not be added during the study except when they were previously not available, and then are able to be obtained.

During the study, dose modification is not permitted except for reasons of documented toxicity or unavailability, except for up-titration of immunosuppressive therapy after a EuroLupus CYC regimen, and taper of corticosteroids as below.

Corticosteroids should be tapered as per local standard of care or practice to a goal of ≤ 10 mg of prednisone by Week 16.

Table 3: Permitted LN Medications During Study

Permitted Medications during study	Max dose	Therapeutic Agent Stability prior to Baseline	Required washout if not continued during study, from Baseline
Prednisone (or other corticosteroid)	60 mg qd (or prednisone equivalent)	14 days	6 weeks
Mycophenolate mofetil	N/A	8 weeks	8 weeks
Mycophenolic acid	N/A	8 weeks	8 weeks
Leflunomide	N/A	8 weeks	8 weeks
Azathioprine	N/A	8 weeks	8 weeks
Cyclosporine	N/A	8 weeks	8 weeks
Tacrolimus	N/A	8 weeks	8 weeks
Methotrexate	N/A	8 weeks	8 weeks
Other oral immunosuppressants/ immunomodulators	N/A	8 weeks	8 weeks

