9.2 Early Withdrawal of Patients from Study

Patients may stop study drug for any of the following reasons:

-
- Patient request/withdraw consent due to an AE
 - Patient request/withdraw consent for any reason other than an AE
 - Patient becomes pregnant
 - Use of non-permitted concurrent therapy
 - Non-compliance with the study drug or study schedule
 - AE of \geq Grade 4
 - Lost to follow-up
 - Occurrence of AEs not compatible with the continuation of patient participation in the study, in the investigator's or sponsor's opinion, or unacceptable to the patient to continue
 - Investigator request
 - Sponsor request

For Phase 1b, patients who do not comply with the protocol or who withdraw consent may be replaced. For Phase 2, only patients who withdraw before the Week14 injection may be replaced.

Patients are free to withdraw from the study at any time without providing reason(s) for withdrawal and without prejudice to further treatment. The reason(s) for withdrawal will be documented in the eCRF. If a patient withdraws consent, all samples obtained will be retained for analysis unless the patient confirms that he or she wishes the samples to be discarded.

Patients withdrawing from the study treatment will be encouraged to complete the Early Withdrawal Visit within 7 days and return for an EOS Visit approximately 12 weeks after receipt of their last dose to complete the final evaluations according to this protocol, particularly safety evaluations. The aim is to record data in the same way as for patients who completed the study.

Reasonable efforts will be made to contact patients who are lost to follow-up. These efforts must be documented in the patient's file.

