11.1.2 Phase 2 Endpoints

Primary Endpoint:

- The number of patients with a 50% reduction in UPCR after 24 weeks of treatment when compared to baseline

Secondary Endpoints:

- Safety and tolerability of KZR-616 as assessed by the incidence, nature, and severity of AEs

-
- The number of patients with a partial renal response (PRR) after 24 weeks of treatment as defined by:
 - a) A 50% reduction of UPCR and/or reduction of UPCR to < 1.0 if the baseline UPCR was < 3.0 or a 50% reduction of UPCR and/or reduction of UPCR to < 3.0 if the baseline was ≥ 3.0
 - b) eGFR of ≥ 60 mL/min/1.73 m² or no worsening of eGFR from baseline of $\geq 25\%$
 - c) No use of prohibited medication
 - The number of patients with a complete renal response (CRR) after 24 weeks of treatment as defined by:
 - a) UPCR of ≤ 0.5
 - b) eGFR of ≥ 60 mL/min/1.73 m² or no worsening of eGFR from baseline of $\geq 25\%$
 - c) Prednisone (or equivalent) < 10 mg
 - d) No use of prohibited medication
 - Time to $\geq 50\%$ reduction in UPCR from baseline
 - Time to CRR
 - Time to PRR
 - Time to UPCR of ≤ 0.5 from baseline
 - The number of patients with UPCR of ≤ 0.5 at 24 weeks
 - The number of patients with daily prednisone (or equivalent) dose ≤ 10 mg
 - Change from baseline in levels of autoantibodies (e.g. ANA, anti-dsDNA) and complement at 24 weeks
 - Changes in corticosteroid use from baseline

Exploratory Endpoints:

- The level of proteasome inhibition in whole blood and PBMCs, as measured by both a cleavable fluorogenic substrate enzymatic assay and a subunit-specific proteasome active site ELISA
- Change from baseline in SLEDAI-2K score, CLASI, and 28 joint count and changes from baseline in laboratory measures
- The proteomic and pharmacogenomic activity of KZR-616 will be assessed through ex vivo analysis of whole blood and PBMC samples
- Serum cytokine levels and circulating leukocytes will be measured in blood samples collected on Day 1 of Weeks 1, 5, 17 and 25

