11.3.6 Handling of Missing Data

All withdrawals will be included in all analyses up to the time of withdrawal. Patients who are withdrawn prematurely from investigational product and/or the study will be included in all analyses regardless of the duration of treatment. There will be no imputation for missing data, unless otherwise specified.

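### The Phase 2 primary endpoint lacks the prohibited-medication condition that PRR and CRR carry, and no analysis in the protocol shows how far permitted flare steroids affect it

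*Combined protocol and SAP*

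**What the plan says.** The primary endpoint is defined three times. The synopsis has "The number of patients with a 50% reduction in UPCr after 24 weeks of treatment when compared to baseline", Section 11.1.2 repeats it, and Section 11.3.5 turns it into a proportion: "The primary efficacy endpoint in Phase 2 is percent of patients with 50% reduction in UPCR after 24 weeks of treatment". Section 11.3.5 then tests a null of at most 20% with an exact binomial test. None of the three mentions other medication.

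In the same endpoint list, PRR and CRR each carry the item "No use of prohibited medication". CRR alone also limits prednisone (below 10 mg in Section 11.1.2, at most 10 mg in the synopsis).

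The conduct sections bear on this as follows:

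- **Excluded drugs (Section 7.2.1, Appendix E):** immunoglobulin, cytokine antagonists, B-cell depletion, other biologics, high-dose or oral cyclophosphamide, investigational agents, plasma exchange and live vaccines. Corticosteroids are not listed.
- **Consequence of use (Section 9.2):** "Use of non-permitted concurrent therapy" is one of the reasons for which study drug may be stopped.
- **Flare steroids (Section 7.2):** "Prednisone (or other corticosteroid) can be initiated or increased to treat a non-renal SLE flare". For Phase 2 the same section adds: "Stable prednisone dose is preferred between Week 16 and Week 24".
- **Flare steroids (Section 7.2.2):** "Corticosteroids should not be added during the study except when needed to treat an SLE flare". This section also bars dose changes during the study, apart from toxicity, supply problems, titration after EuroLupus cyclophosphamide and steroid taper.
- **Withdrawals (Section 11.3.6):** such patients "will be included in all analyses regardless of the duration of treatment". The sentence before it limits their inclusion to the period before withdrawal.

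Section 11.3.5 refers to a separate SAP for details, and Section 11.3.1 gives that SAP precedence. Its text is not in the supplied document.

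**The concern.** Phase 2 is a single-arm, open-label study of 20 patients judged against a fixed 20%. With no control arm, a fall in UPCR brought about by another active drug cannot be told apart from one brought about by KZR-616. The protocol guards against this for both secondary response endpoints but not for the primary one, so the same patient could be a success on the primary endpoint and a failure on PRR and CRR solely because of a prohibited drug.

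Permitted flare steroids raise a milder form of the same problem. Section 7.1.3 itself warns, for steroids given against injection reactions, that they may blur the efficacy reading. Phase 1b requires a stable prednisone dose in Weeks 9 to 13. Phase 2, where efficacy is primary, only prefers one in Weeks 16 to 24. Section 2.5 expects pivotal lupus nephritis studies to follow from the Phase 2 results.

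**Working it through.** **1. The definitions side by side (Section 11.1.2).**

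| Condition | Primary | PRR | CRR |
|---|---|---|---|
| UPCR criterion | yes | yes | yes |
| eGFR criterion | no | yes | yes |
| Prednisone limit | no | no | yes |
| Prohibited medication excluded | no | yes | yes |

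**2. Can a prohibited-drug user be scored a primary responder?** The assessment after 24 weeks is the Week 25 visit, Day 169 (24 × 7 + 1 = 169), when a 24-hour urine is collected (Section 8.2.6.5, Appendix B). Under Section 9.2, use of a non-permitted drug may end study treatment but does not have to. A patient who stays on KZR-616 has a Week 25 UPCR, and nothing in the three definitions bars that patient from being a responder.

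**3. Flare steroids.** A new course for a non-renal flare is allowed by Sections 7.2 and 7.2.2 and is absent from Appendix E, so neither the primary endpoint nor PRR excludes it. An increase in a patient already on steroids is less clear: Section 7.2 allows it, while Section 7.2.2 limits dose changes and makes its flare exception for steroids that are added.

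**4. Weight of one patient.** The plan gives no alpha, power or flare rate, so there is no figure of its own to reproduce. Inputs are n = 20 (Section 5.1) and p0 = 0.20 (Section 11.3.5). The test is one-sided because the alternative is above 20%:

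P(X ≥ r) = Σ C(20, k) × 0.2^k × 0.8^(20−k), summed over k = r to 20.

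| Responders | Exact p |
|---|---|
| 7/20 | 0.0867 |
| 8/20 | 0.0321 |
| 9/20 | 0.0100 |
| 10/20 | 0.0026 |
| 11/20 | 0.0006 |

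With 18 observed patients (an assumption), 8/18 gives 0.0163 and 7/18 gives 0.0513. From 11/20 upward, reclassifying one patient does not alter the reading (0.0006 to 0.0026).

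**5. Illustrative range.** Let the KZR-616 response rate equal the null of 20%, let a share f of patients receive another active therapy, and let q be the chance that such a patient, otherwise a non-responder, reaches a 50% fall. The apparent rate is 0.20 + 0.80 × f × q. Both f and q are assumptions, and only the upward mechanism is modelled.

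| f | q | Apparent rate | P(X ≥ 8) |
|---|---|---|---|
| 0 | – | 20% | 0.032 |
| 5% | 25% | 21% | 0.042 |
| 5% | 100% | 24% | 0.084 |
| 10% | 25% | 22% | 0.054 |
| 10% | 100% | 28% | 0.171 |

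The cut-off of 8 is illustrative.

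**6. Price of a non-responder rule.** If a rule turned one true responder in 20 into a failure (1/20 = 5 percentage points, say 40% to 35%), the chance of reaching 8/20 would fall from 0.584 to 0.399.

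**The case against.** The strongest reply is that the details belong in the SAP, which takes precedence and was not available. That stands as a limit: if the SAP already has a medication rule for the primary endpoint, this point falls away. The protocol's own definition is nevertheless silent in three places where the neighbouring endpoints are not.

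A second reply is that Phase 2 studies KZR-616 on top of standard therapy, so counting the outcome whatever permitted care was given is a legitimate choice. This also stands, for flare steroids. A reader might infer that every patient given flare steroids must be a primary non-responder, but the documents do not support that. Steroid exposure is also reported through the CRR limit, the number of patients at 10 mg or less, and the change in corticosteroid use.

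Three other stronger readings should be resisted:

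- **Withdrawn users of prohibited drugs remain responders.** Section 11.3.6 does include withdrawn patients whatever their treatment duration, but it also limits them to the time before withdrawal. Section 9.2 sends those who stop to a visit within 7 days and another about 12 weeks after the last dose. Continued planned assessments are stated only for stops due to adverse events (Section 7.1.4). This route is doubtful and is not relied on here.
- **PRR misses all flare steroids.** That is clear only for newly started courses. Increases are unsettled, as step 3 shows.
- **The response rate is inflated.** The encouraged taper to 10 mg or less by Week 16 could push UPCR the other way, so the net steroid effect is unknown.

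Finally, sensitivity to one patient is a feature of any binary endpoint at n = 20. It shows what a reclassification would be worth, not that one will happen.

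**Conclusion.** The point holds in two parts. First, as written, the primary endpoint can count a patient who used an Appendix E drug as a responder when PRR and CRR would not. Adding the condition can only lower the responder count or leave it unchanged. Second, permitted steroid starts for a non-renal flare are excluded by neither the primary endpoint nor PRR. That is defensible for the main analysis, but the protocol plans no analysis that shows its influence.

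The size is not known: the documents give no rate of prohibited-drug use or flares, no alpha and no source for the 20%. If the 20% already reflects care that includes flare steroids, the second part matters less. One patient is decisive only near the margin, at about 7 to 9 responders of 20. The conclusion assumes that prohibited medication means the drugs in Section 7.2.1 and Appendix E, and that the separate SAP has no such rule.

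**What to change.** Unless the SAP already covers this:

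1. **Primary endpoint.** State in Sections 11.1.2 and 11.3.5 that a patient who used prohibited medication, defined as Section 7.2.1 and Appendix E, before the Week 25 UPCR is a non-responder. Use the same definition for PRR and CRR. This settles the scoring without deciding the clinical question left open between Sections 7.2 and 7.2.2.
2. **Permitted flare steroids.** Keep these patients as observed in the primary analysis. Pre-specify a sensitivity analysis of the primary endpoint and PRR that counts as non-responders those whose systemic corticosteroid was started, or raised above the lowest dose reached earlier in the study, between Week 16 and the Week 25 UPCR. Leave out single premedication doses under Section 7.1.3. List all flare-steroid courses beside each patient's UPCR result.

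The reference should be the lowest earlier dose, not baseline. Entry doses may be as high as 60 mg, so a patient who starts at 40 mg, tapers to 10 mg and returns to 40 mg at Week 20 would never exceed baseline.

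The cost is a short paragraph. Concomitant therapy is already recorded (Section 7.2) and UPCR is already collected at Week 25 (Section 8.2.6.5). The sensitivity analysis needs only doses and dates. The listing also needs the reason for each course. The protocol does not say whether that is captured; if it is not, list every new or increased course.

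The downside is that a true responder who took a prohibited drug for a non-renal reason becomes a failure, so the primary rate may be slightly lower. Step 6 shows what one such patient in 20 could cost.
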